### **7.11.2 Withdrawal from the trial**

Participants have the right to withdraw at any time. Participants who formally withdraw from the study at any point will not receive any further contact from the study team. Participants who withdraw before Visit 2 (Baseline) will be replaced by assigning successive screening IDs to eligible subjects, but after completing randomisation on visit 2 participants will not be replaced due to the planned intention to treat analysis.

In addition the investigator may withdraw a participant from the study at any time if it is considered necessary for any reason including:

- Ineligibility (either arising during the study or retrospective)
- Significant protocol deviation
- Significant non-compliance with treatment or study requirements
- An adverse event which results in inability to continue to comply with study procedures
- Disease progression which results in inability to comply with study procedures
- Consent withdrawn, loss of capacity or detention under Mental Health Act
- Failure to respond to contact attempts from the study team
- Pregnancy

The reason for participant withdrawal will be recorded in the case report form (CRF).

### **7.11.3 Stopping rules**

The trial may be stopped before completion for the following reasons:

- If the CI and/or sponsor decide to suspend the trial pending safety review of an emergent issue
- The CI and /or sponsor decide to stop the trial for safety, administrative or other reasons

## **8 Name and description of all drugs used in the trial**

### **8.1 Treatment of subjects**

Investigational product/treatment

Participants will receive the following:

1. 3 x weekly infusions of IV ketamine hydrochloride (Ketalar®) at a dose of 0.8mg/kg over 40 mins, or
2. 3 x weekly infusion of placebo (50ml Saline 0.9%) over 40 mins.
3. Ketamine is packaged as: Ketalar® glass vial with rubber closure and aluminium flip-off cap containing. Exipients with known effects: Each 1 ml contains 2.6 mg of sodium. The total amount to be delivered will be calculated on the basis of the patient's weight (0.8 mg/kg). Site pharmacy will order ketamine and dispense per patient, added to saline (0.9%) to make up to 50ml solution in syringes for the infusion pump to infuse intravenously. Doses will be administered using a computer controlled infusion pump.

Placebo will be 50 ml saline (NaCl) 0.9% in syringes for the infusion pump.

## 8.2 Concomitant medication

Ketamine interacts with the following substances and therefore their concomitant use will not be permitted during active treatment days: barbiturates and/or narcotics, atracurium and tubocurarine, central nervous system (CNS) depressants (e.g. phenothiazines, sedating H1 – blockers or skeletal muscle relaxants), thiopental, thyroid hormones, antihypertensive agents, theophylline and other methylxanthines.

Due to potential impacts on the primary outcomes taking any other relapse prevention medication or anti-depressants will not be permitted during the period of study (Visit 2 - Visit 8).

Other concomitant medication use will be recorded in the CRF.

## 9 Investigational Medicinal Product

### 9.1 Name and description of investigational medicinal product(s)

The product under test will be three weekly doses of ketamine hydrochloride (Ketalar®) at a dose of 0.8mg/kg I.V. over 40 minutes. Ketalar® 10mg/ml or 50mg/mL Injection vials will be used. Ketamine is a Controlled Drug (Schedule 4, Part 1). Placebo will be saline (0.9%) given I.V. over 40 mins.

Doses will be made up from Ketalar® neutral glass vial with rubber closure and aluminium flip-off cap containing ketamine hydrochloride. The Marketing License holder is Pfizer.

### 9.2 Name and description of each NIMP

N/A No NIMPs to be used in this trial

### 9.3 Summary of findings from non-clinical studies

*Please refer to the Summary of Product Characteristics (SPC) and Section 2.1.*

### 9.4 Summary of findings from clinical studies

*Please refer to the Summary of Product Characteristics (SPC) and Section 2.3.*

## **9.5 Summary of known and potential risks and benefits**

*See Section 2.4 and 2.5 and Summary of Product Characteristics.*

## **9.6 Description and justification of route of administration and dosage**

Ketamine will be administered at a dose of 0.8mg/kg IV over 40 mins using an infusion pump. The original study of ketamine for relapse prevention in alcoholics used a high IM bolus dose (2.5mg/kg), however our collaborator [name] suggested the use of a lower dose in alcohol dependence (1.2mg/kg IM) which data from a small sample (n=15) suggests was also effective. The lowest dose of ketamine that is likely to be effective is clearly preferable to minimise psychotomimetic effects which may reduce treatment tolerability and increase risk of drop-out. The proposed dose is higher than that routinely used in patients with treatment refractory depression (usually 0.5mg/kg IV see 43 for a review) but well within the range of doses that increase synaptogenesis in preclinical studies (up to 30 mg/kg IP). Similar doses have also been used successfully in treatment resistant depression (1.0mg/kg IM: 95). The reasons for use of this higher dose is that, given the better bioavailability of ketamine IV, this dose roughly equates to the lowest effective IM bolus dose in alcohol dependent patients used by our collaborator EK. The conversion of IM to IV dose was based on extrapolation of pharmacokinetic (PK) data [96; 97] as well as consultation with [name] (Cambridge / Groningen) who has investigated the PK profile of ketamine. We have opted for an IV route of administration as the effects are more easily controlled by the clinician, i.e. the duration of effects are shorter, and there is less variability in Cmax [99]. Placebo will be 50ml saline (0.9%) given IV over 40 mins using an infusion pump.

## **9.7 Dosages, dosage modifications and method of administration**

Patients will be administered three doses of 0.8 mg/kg ketamine IV or three doses of the placebo (50ml Saline 0.9%) given IV over 40 mins through computer controlled infusion pump. As dose will be tailored to weight of participants, the site pharmacy or delegated unblinded site staff on the ward will prepare individualised doses according to the randomisation and patient individual weight.

## **9.8 Preparation and labelling of Investigational Medicinal Product**

Preparation and labelling of the investigational medicinal products should be completed in accordance with Annex 13 of Good Manufacturing Practice (GMP) guidelines. Labelling exemption will apply and a dispensing labelling (as defined in the SoDA) will be used.

The prepared IMP and Placebo will be labelled with the approved templates provided by the sponsor.

## **9.9 Drug accountability**

Routine hospital stocks of ketamine and saline will be used for this trial. A drug inventory/dispensing record will be maintained and updated by the authorised unblinded personnel at pharmacy or delegated unblinded site staff on the ward for all drugs provided and dispensed at each study site. At the end of the study, one copy of the drug inventory/dispensing record should be sent to the sponsor, one kept in the central study file and one in the site files. An unblinded person at each study site is responsible for all drug supplies. Written documentation is mandatory.

The unblinded persons at the sites will keep adequate records of the receipt, preparation, administration and return or destruction of the study medication. They will conceal the accountability forms to blinded personnel and ensure these logs are maintained and kept in the pharmacy file at site. All data regarding the study medication must be recorded on the relevant forms provided by the sponsor or local pharmacy accountability forms. Any dispensed but completely unused infusions (where the infusion bag has not been opened) at the London site will be returned to pharmacy and destroyed in line with site pharmacy procedures. Partially unused infusions at the London site cannot be accepted by pharmacy. Therefore the local controlled drug policy will be followed at the Clinical Research Facility to ensure that materials are appropriately destroyed. Completely unused or partially unused infusions at the Exeter site cannot be accepted by pharmacy and are therefore destroyed at the Clinical Research Facility. In all instances a record of this destruction will be kept in accordance with relevant SOPs, to document the return and/or destruction of materials at site.

## **9.10 Source of IMPs including placebo**

The IMP will be sourced from routine hospital stock and their handling and management will be subject to standard procedures of the pharmacy. Sourcing of IMP is also discussed in the Summary of Drug Arrangements. The following IMPs and placebo can be used from routine hospital stock and their handling and management will be subject to standard procedures of the Pharmacy:

- IMP (Ketamine): Ketalar®
- Placebo (Saline 0.9 %) hospital stocks and any brand can be used as long as they are licensed for use within the UK.

### **9.11 Dose modifications**

No dose modification will be permitted. If intolerable side effects are experienced, the subject will be withdrawn from IMP treatment (see also section 7.11).

### **9.12 Assessment of compliance**

Compliance includes both adherences to IMP and Protocol study procedures. The trial medication will be administered by the research anaesthetist only in the context of the patient attending the Clinical Research Facility. Patients will not be responsible for any trial medication. A member of the research team will ensure that the arrangements for each treatment visit are agreed with the participant and their carer. Where necessary, the researcher will assist in transportation. If a participant fails to attend a clinic visit for the infusion then the researcher will endeavour to contact the patient to identify the reason. Where possible an alternate appointment will be made within the infusion visit window (see Appendix B). If the participant fails to attend a clinic visit for the follow-up day the researcher will endeavour to contact the patient to identify the reason and where possible arrange an alternative visit within the follow up visit window (see Appendix B). All episodes of failure to attend will be recorded in the medical notes, CRF and protocol deviation log. If the participant misses 2 consecutive infusions, then they will be withdrawn from treatment and will be invited to attend follow up visits 9 and 10 as part of our intention to treat protocol. Noncompliance to the Protocol study procedures will be documented by the investigator and reported to the Sponsor as agreed. Persistent noncompliance (<80%) may lead the patient to be withdrawn from the study.

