## 7.2 Randomisation procedures

A blocked design for randomisation will be used to allocate patients using a 1:1:1:1 ratio for the 4 respective groups. Randomisation will be performed by a specialist company ([www.sealedenvelope.com](http://www.sealedenvelope.com)) who will hold the randomisation list and provide 24/7 internet access for unblinding services. Early drop-outs (during screening and the baseline week up until randomisation) will be replaced. Once patients have been randomised at week 0 they will not be replaced regardless of compliance or dropout status and will be analysed as part of the intention to treat analysis. After randomisation, the site research team will be given a unique trial randomisation code via email from [sealedenvelope.com](http://sealedenvelope.com). This code corresponds to an envelope at the site which contains the treatment allocation. These envelopes will be provided by the trial statistician at the start of the trial and are kept in a secure location by allocated partially unblinded staff. The trial statistician will be provided the treatment allocation codes prior to the start of the trial to prepare the envelopes. Separate envelopes will be provided for the delegated staff preparing the IMP (containing the IMP treatment allocation) and the psychology staff (containing the psychological treatment allocation). To protect the blind, pharmacy or delegated unblinded staff preparing the IMP at site will be notified separately via email of the randomisation code. An additional email is sent to the psychology team at site who can refer to the correct envelope to determine the psychological treatment allocation. Randomisation details of patients will be entered on a trial Subject Log and will follow the instructions set out in a Standard Operating Procedure (SOP) on randomisation. Data review will take place when half the target samples have been randomised. Upon randomisation, patients will be given a study specific patient card which will have study title, IMP details, patient ID and contact details of the out of hours contact in cases of emergency.

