Breathalyser tests will be used at each visit for the following reasons:

- Screening & re-screening – To assess eligibility
- Baseline visit (1st infusion) – To assess eligibility/ensure safety of IMP administration/ensure patient is able to complete cognitive tasks and questionnaires, as well as engage with therapy/education
- Visit 3, 5, 7 & 8 – To ensure patient is able to complete cognitive tasks and questionnaires, as well as engage with therapy/education
- Visit 4 & 6 (2nd & 3rd infusion) – To ensure safety of IMP administration/ensure patient is able to complete cognitive tasks and questionnaires, as well as engage with therapy/education
- Visit 9 & 10 - To ensure patient is able to complete cognitive tasks and questionnaires

Once randomised, if a patient attends for any visit and does not blow 0 on the breathalyser the visit will be terminated (either for the primary purpose of safety on infusion visits or of data integrity on non-infusion visits) and the patient invited to re-attend to complete the visit within the allocated visit window.

Concomitant Medication: All prescription medication, over-the-counter medication, vitamins, and/or herbal supplements will be recorded on case report forms (CRFs).

Vital Signs: Resting pulse, pulse oximetry and blood pressure (BP) measurements will be measured at each visit phase for safety monitoring. Vital signs will be continuously monitored throughout the infusion until the participant has recovered. This monitoring will be recorded on a standard

observation chart, stored as source data. The eCRF will record 3 sets of readings, one prior to the infusion, another after the infusion terminates, and then finally after the participants recovery.

Physical Examination: Height, weight and oral/tympanic temperature will be recorded.

At screening a physician will perform a physical examination of the cardiovascular, respiratory, GI and neurological system to a level of detail that would be expected for a patient due to receive anaesthesia.

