### **7.11.1 Discontinuation from treatment**

The investigator may discontinue a patient from treatment if it is considered necessary for any reason including:

- Ineligibility (either arising during the study or retrospective)
- Significant protocol deviation e.g. if treatment is stopped for longer than 21 days (All protocol deviations and violations will be recorded and reported to the sponsor)
- Significant non-compliance with treatment or study requirements e.g. If the participant misses 2 consecutive infusions, as detailed in section 9.12
- An adverse event which requires discontinuation of the study medication or results in inability to continue to comply with study procedures
- Disease progression which requires discontinuation of the study medication
- Pregnancy
- In the case of an overdose (see section 10.5.5)

Where treatment is discontinued, participants will be invited to attend follow up visits 9 & 10 on the basis of our planned intention to treat analysis which assumes (and formally tests: see section 13.3.4) that data are missing at random.

The reason for participant treatment discontinuation will be recorded in the case report form (CRF).

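### Non-compliance or protocol deviation may lead to investigator withdrawal from the whole study with no follow-up stated, while other rules treat the same triggers as stopping treatment only

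*Protocol*

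**What the plan says.** Protocol 9.12 defines its terms broadly: "Compliance includes both adherences to IMP and Protocol study procedures". For a participant who misses two consecutive infusions it says "they will be withdrawn from treatment and will be invited to attend follow up visits 9 and 10", and gives intention to treat as the reason. Its last sentence goes further: "Persistent noncompliance (<80%) may lead the patient to be withdrawn from the study".

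Section 7.11.1 covers stopping treatment. Its reasons include "Significant non-compliance with treatment or study requirements e.g. If the participant misses 2 consecutive infusions, as detailed in section 9.12" and significant protocol deviation. Participants whose treatment is discontinued are invited to visits 9 and 10.

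Section 7.11.2 covers leaving the trial. After the participant's own right to withdraw, it adds: "In addition the investigator may withdraw a participant from the study at any time if it is considered necessary for any reason including". The list that follows repeats significant protocol deviation and significant non-compliance, and says nothing about visits 9 and 10.

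Section 7.2 says of randomised patients that "they will not be replaced regardless of compliance or dropout status and will be analysed as part of the intention to treat analysis". The opening of 7.11 promises every effort to keep participants in the study and to continue assessments.

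**The concern.** An investigator facing a poorly compliant participant has two routes. One keeps the 6-month outcome; the other does not say that it does. The choice is made after randomisation and no criterion is given for it.

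Non-compliance here may be linked to the outcome. Section 7.9.1 says that after randomisation "if a patient attends for any visit and does not blow 0 on the breathalyser the visit will be terminated". The patient is invited to re-attend within the visit window, but a visit that is not completed in time becomes a missed study procedure, which 9.12 counts under compliance. Withdrawal for non-compliance could therefore select on drinking.

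The primary analysis is complete case (Protocol 13.3.2; SAP 4.5 and 6.5), so a participant without a 6-month outcome drops out of it. Multiple imputation is the only planned response to missing primary outcomes. Protocol 13.3.4 bases it on missing at random, and no alternative assumption is examined. Section 7.11.1 says that this assumption is formally tested in 13.3.4, but 13.3.4 only makes it.

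Two other results are exposed. The Summary uses drop-out as the indicator of tolerability, which is part of a primary objective, and 13.3.3 reports attrition as a feasibility outcome. Both would mix investigator withdrawals with genuine drop-out.

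**Working it through.** **The rules side by side**

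| Trigger | Section | What ends | Visits 9 and 10 |
|---|---|---|---|
| Two consecutive infusions missed | 9.12, and the example in 7.11.1 | Treatment | Invited |
| Significant non-compliance | 7.11.1 | Treatment | Invited |
| Significant non-compliance | 7.11.2 | Study (discretionary) | Not stated |
| Significant protocol deviation | 7.11.1 | Treatment | Invited |
| Significant protocol deviation | 7.11.2 | Study (discretionary) | Not stated |
| Persistent non-compliance below 80% | 9.12, last sentence | Study (discretionary) | Not stated |

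**What 80% could mean.** The result depends on what is counted:
- 3 infusions: one missed is 2/3 = 66.7%; two missed is 1/3 = 33.3%.
- 7 therapy or education sessions: one missed is 6/7 = 85.7%; two missed is 5/7 = 71.4%.
- 9 visits (2 to 10): one missed is 8/9 = 88.9%; two missed is 7/9 = 77.8%.

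If infusions are counted, anyone who misses two in a row meets both the keep-in-follow-up rule and the below-80% threshold. If visits are counted, one missed infusion visit stays above it.

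**The plan's own figure.** Protocol 13.2.1 assumes relapse of 50% on placebo and 25% on ketamine with 24 per drug arm after 50% drop-out. The 90% interval for the difference is 0.25 ± 1.645 × √(0.5×0.5/24 + 0.25×0.75/24) = 0.25 ± 0.222, or 2.8% to 47.2%. This reproduces the stated 3% to 47%.

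**Bias in the complete-case relapse rate.** Let P be the arm's true relapse rate, f the fraction withdrawn and r the relapse rate among those withdrawn. The documents give neither f nor r; both are assumed.

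Observed rate = (P − f·r)/(1 − f). If r = P, this equals P and there is no bias.

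*No true effect (P = 50% in both arms), withdrawal 10 points higher on ketamine.* Differences are from unrounded rates.

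| f placebo / ketamine | r | Placebo | Ketamine | Difference (points) | RR |
|---|---|---|---|---|---|
| 0% / 10% | 75% | 50.0% | 47.2% | 2.8 | 0.94 |
| 0% / 10% | 100% | 50.0% | 44.4% | 5.6 | 0.89 |
| 5% / 15% | 75% | 48.7% | 45.6% | 3.1 | 0.94 |
| 5% / 15% | 100% | 47.4% | 41.2% | 6.2 | 0.87 |
| 10% / 20% | 75% | 47.2% | 43.8% | 3.5 | 0.93 |
| 10% / 20% | 100% | 44.4% | 37.5% | 6.9 | 0.84 |

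Swapping the arms reverses the sign and inverts the relative risks: 1/0.944 = 1.06 to 1/0.844 = 1.19. Ten points is 4.8 of the 48 randomised per drug arm.

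*True effect as planned (50% and 25%).* With the same f and r in both arms, the difference becomes 0.25/(1 − f): 26.3 points at f = 5% and 31.2 at f = 20%. For r of 75% to 100% the RR moves from 0.50 to between 0.46 (f = 5%, r = 75%) and 0.17 (f = 20%, r = 100%).

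If instead a fraction w of relapsers alone is withdrawn, the observed rate is P(1 − w)/[P(1 − w) + 1 − P]. With w = 40% in both arms, the rates are 0.15/0.90 = 16.7% and 0.30/0.80 = 37.5%. The difference falls to 20.8 points while the RR moves to 0.44. With w = 20% on ketamine and 40% on placebo, they are 0.20/0.95 = 21.1% and 37.5%; the difference is 16.4 points and the RR 0.56.

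The direction therefore depends on the assumptions and on whether the difference or the relative risk is read. The relative risk is the planned estimate.

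**The case against.** The best defence is that the follow-up route already exists: 7.11.1 offers visits 9 and 10 after treatment is stopped for these same triggers, and the study-withdrawal power is discretionary and may rarely be used. That limits how often the problem would arise. It does not settle which route applies, because 7.11.2 repeats the triggers without the invitation.

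Several stronger readings are tempting, and the documents do not support them:
- **That these participants are never contacted again.** The no-contact sentence in 7.11.2 is worded for participants who formally withdraw. Investigator withdrawal is introduced separately, and contact afterwards is not addressed.
- **That 9.12 flatly contradicts itself.** One rule has a definite trigger; the other is a discretionary power for persistent non-compliance. They overlap without being reconciled.
- **That those removed are the likeliest to have relapsed.** This is an inference from the breathalyser rule. A positive reading leads to an invitation to re-attend; the windows for visits 4, 6 and 8 run from 4 to 21 days after the preceding infusion visit. Nor is any positive reading a relapse as defined (5 drinks for men or 4 for women on one occasion).
- **That the 3-month stopping rule is compromised.** It needs more than 21/24 (Protocol 13.5) or 42/48 (SAP 6.1) lost, about 88%. Occasional compliance withdrawals would hardly affect it.
- **That imputation must fail.** Timeline follow-back at visits 2, 4, 6 and 8 and SCRAM-X monitoring during treatment could make missing at random reasonable if the model used them. The documents do not specify the model, and later drinking in someone no longer followed is unobserved.

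Blinding of outcome collectors to drug (SAP 4.4) makes deliberate differential withdrawal by drug unlikely. It does not stop attendance itself from differing between arms.

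Ineligibility also appears in both lists, but SAP 4.7 excludes participants found ineligible after randomisation from all analyses. Changing that ground alone would alter no result, so it is left out here.

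**Conclusion.** The point holds as an unreconciled overlap that permits avoidable loss of 6-month outcomes for non-compliance or protocol deviation, on grounds that drinking can influence. Neither the frequency of such withdrawals nor the relapse rate among them is known. The illustrated bias under no true effect, about 3 to 7 points either way (RR roughly 0.84 to 1.19), rests on a 10-point difference in withdrawal between arms and on 75% to 100% of those withdrawn having relapsed. It is small beside the ±22-point half-width of the planned 90% interval, and zero if those withdrawn relapse at the arm rate. A reader might infer that the rule favours ketamine; the calculations show no fixed direction. Precision is not the main issue, since the plan already allows for 50% drop-out, and the inferential analyses are labelled exploratory. The change is a cheap improvement: it prevents the loss at source, and it keeps the attrition and tolerability figures interpretable.

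**What to change.** In Protocol 9.12 and 7.11.2, remove non-compliance and protocol deviation as grounds for investigator withdrawal from the study. State that they may end treatment under 7.11.1 but do not end outcome collection: these participants are invited to visits 9 and 10 and asked for timeline follow-back, by telephone if needed, unless they withdraw consent to follow-up. Section 11.2 already provides for telephone completion of missing questionnaire items. Report withdrawals by arm and reason, separating investigator decisions from the participant's own. Leave the treatment-discontinuation rules unchanged.

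The cost is protocol wording and a few more follow-up contacts within the existing visits.
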